10.11 APPENDIX 11: SIMULATION REPORT – ASSESSMENT OF PERFORMANCE

In Part-1 and Part-3A, there are not many dose levels included in the dose escalation. Therefore, interval design, specifically mTPI2, will be used in the dose escalation process.

The goal of assessing the mTPI2 design's performance is to evaluate its overall operating characteristics by comparing with 3+3 design under a range of scenarios for hypothetical DLT dose-response relationship that may occur during the conduct of the study. Here, the performance comparison of mTPI2 and 3+3 is presented for Part-1. Since the mTPI2 and 3+3 designs both consider doses in a discrete space, the performance comparison will be considered similar for Part-1 and Part-3A.

SPECIFICATION OF SIMULATION SCENARIOS

The planned starting dose levels are 100 mg (Dose level 1), 140 mg (Dose level 2) and 200 mg (Dose level 3). The first cohort will start with 140 mg.

Four scenarios were defined for DLT rate at all dose levels as shown in [Figure 6](#). The scenarios were selected to represent a wide range of possible cases: the true MTD is dose level 2 (Scenario 2 and 3), dose level 3 (Scenario 1) and even higher than dose level 3 (Scenario 4).

Please note that it is strongly believed that the chance of dose level 1 being the MTD is extremely low based on the monotherapy results. Therefore, the scenario of dose level 1 being the MTD is not in the consideration. Also, the Scenario 2 and 3 have the same DLT trend. They cover the lower and upper bounds of the target toxicity interval at dose level 2. In order to make the plot self-explained, indicators will be used along with each scenario. For each dose level, “L” indicates low rate of DLT, and “T” indicates target rate of DLT which refers to MTD. “H” indicates high rate of DLT. For example, Scenario 1 would be indicated as LLT while Scenario 4 would be indicated as LLL.

PERFORMANCE

To evaluate the design performance for the 4 scenarios described above, the following measures will be discussed.

- Probability of a dose level selected as MTD
- Mean number of participants treated at each dose level

Results based on n=1000 simulated trials. The target DLT rate is set to be █.

Abbreviations: DLT = dose-limiting toxicity, H = high rate of DLT, L = low rate of DLT, T = target rate of DLT which refers to MTD

Using the hypothetical scenarios specified above, the results for mTPI2 are plotted in [Figure 7](#) and [Figure 9](#). The results from 3+3 design are presented in [Figure 8](#) and [Figure 10](#) for a comparison purpose.

In general, mTPI2 design can find the true MTD more accurately than the 3+3 design. The 3+3 design is more conservative than the mTPI2. The chance of finding the correct MTD (in red) is higher than any other dose level for all scenarios in mTPI2 design. While in Scenario 2 and 3, 3+3 design is much conservative to recommend the 100 mg as MTD in more than [REDACTED] of simulated trials. Specifically, when the true DLT rate changes from [REDACTED] in Scenario 2 to [REDACTED] in Scenario 3, the 3+3 design will recommend 100 mg from [REDACTED]. The mTPI2 recommends the 140 mg as MTD consistently ([REDACTED]) in both scenarios. In Scenario 1, the 3+3 design is not able to differentiate 140 mg and 200 mg when the true MTD is 200 mg ([REDACTED]). Even in Scenario 4 where the true MTD is >200 mg, the 3+3 design still identify the MTD as <100 in [REDACTED] of the simulations. Also, when 2 DLTs were observed out of 3 participants, the 3+3 design will claim the MTD has to be lower than the current dose level while the mTPI2 design will just recommend a lower dose level for the next cohort but keep the decision of recommending the current dose level open. Overall, the accuracy of mTPI2 is satisfactory and 3+3 is too conservative.

The sample size needed for both designs are roughly 3 cohorts (9 participants) for all scenarios. But more participants are treated at a dose level below the MTD in 3+3 compared to mTPI2 ([REDACTED]) because 3+3 is too conservative.

[figure not shown]
To conclude, mTPI2 design can provide a more accurate MTD recommendation compared to 3+3 design with similar sample size.

Figure 7 - Probability of a dose level selected as MTD for mTPI2

[figure not shown]
[figure not shown]
Abbreviations: H = high rate of DLT, L = low rate of DLT, MTD = maximum tolerated dose, mTPI2 = modified toxicity probability interval 2, T = target rate of DLT which refers to MTD

Figure 8 - Probability of a dose level selected as MTD for 3+3

Abbreviations: H = high rate of DLT, L = low rate of DLT, MTD = maximum tolerated dose, T = target rate of DLT which refers to MTD

Figure 9 - Mean number of participants per dose level for mTPI2

Abbreviations: H = high rate of DLT, L = low rate of DLT, MTD = maximum tolerated dose, mTPI2 = modified toxicity probability interval 2, T = target rate of DLT which refers to MTD

Figure 10 - Mean number of participants per dose level for 3+3

Abbreviations: H = high rate of DLT, L = low rate of DLT, T = target rate of DLT which refers to MTD

10.12 APPENDIX 12: CONTINGENCY MEASURES FOR A REGIONAL OR NATIONAL EMERGENCY THAT IS DECLARED BY A GOVERNMENTAL AGENCY

A regional or national emergency declared by a governmental agency (eg, public health emergency, natural disaster, pandemic, terrorist attack) may prevent access to the clinical trial site.

- Contingency procedures are suggested below for an emergency that prevents access to the study site to ensure the safety of the participants, to consider continuity of the clinical study conduct, protect trial integrity, and assist in maintaining compliance with Good Clinical Practice in Conduct of Clinical Trials Guidance. Sponsor agreement MUST be obtained prior to the implementation of these procedures for the duration of the emergency.
- During the emergency, if the site will be unable to adequately follow protocol mandated procedures, alternative treatment outside the clinical trial should be proposed, and screening, enrollment, and administration of study intervention may be delayed.
- Attempts should be made to perform all assessments in accordance with the approved protocol to the extent possible. In case this is not possible due to a temporary disruption caused by an emergency, focus should be given to assessments necessary to ensure the safety of participants and those important to preserving the main scientific value of the study.
- Procedures to be considered in the event of a regional or national emergency declared by a governmental agency:
 - If onsite visits are not possible, remote visits (eg, with home nurses, home health vendor, etc) may be planned for the collection of possible safety and/or efficacy data.
 - If onsite visits are not possible, visit windows may be extended for assessment of safety and/or efficacy data that cannot be obtained remotely.
 - Use of local clinic or laboratory locations may be allowed.
 - Contingencies implemented due to emergency will be documented.
 - The participant may be verbally informed prior to initiating any changes that are to be implemented for the duration of the emergency (eg, study visit delays/treatment extension, use of local labs).

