2.3.1.5 Potential risk for SAR442720 and adagrasib administration

SAR442720 is identified as a CYP3A and P-gp substrate, with CYP3A contributing to approximately 45% of total hepatocyte metabolism. Adagrasib is a strong inhibitor of CYP3A and a weak inhibitor of P-gp, which may increase SAR22720 exposure by up to 2-fold (mainly due to CYP3A inhibition). Starting dose of SAR442720 was reduced to 50% of its RP2D from monotherapy and Part-1 of this study. In addition, adagrasib will be started at the lower dose (400 mg BID rather than 600 mg RP2D).

SAR442720 is not anticipated to alter the PK of adagrasib, because SAR442720 has no effect on CYPs and transporters. Overlapping toxicities such as gastrointestinal toxicities are anticipated between the 2 drugs, hence such toxicities may occur more frequently than in the monotherapy settings. It is not known whether QT prolongation may occur more frequently with the combination therapy, however this cannot be excluded at this stage.

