The dose of SAR442720 will be escalated or de-escalated depending on the emerging safety data of the combination. The starting dose (dose level 1 [DL1]) of SAR442720 will be 100 mg BIW, which is 50% of the highest cleared dose in the ongoing Phase 1 monotherapy dose escalation study (<https://clinicaltrials.gov>; NCT03634982). DL2 (140 mg BIW) and DL 3 (200 mg BIW) for SAR442720 have been cleared in the ongoing Phase 1 monotherapy dose escalation study. The adagrasib starting dose (DL1) will be 400 mg BID orally, which is one dose level below the RP2D in monotherapy (3). Refer to [Table 14](#) below for dose escalation. At least 6 participants need to be treated at the MTD and RP2D.

Table 14 - Dose escalation for Part-3A

Dose Level	SAR442720 (BIW)	Adagrasib (daily)
Part-3 – DL(-)1	80 mg D1, D2	400 mg BID
Part-3 – DL1 (starting dose)	100 mg D1, D2	400 mg BID
Part-3 – DL2	140 mg D1, D2	400 mg BID
Part-3 – DL3a ^a	140 mg D1, D2	600 mg BID
Part-3 – DL3b ^a	200 mg D1, D2	400 mg BID
Part-3 – DL4	200 mg D1, D2	600 mg BID

Abbreviations: BID, twice daily; BIW, twice a week; D, day; DL, dose level.

^a DL3b is optional and may be recommended by the study committee according to the safety data before further escalating to DL4.

Overall safety monitoring will be performed throughout the conduct of the study. Additional dose levels and/or additional schedules of administration can be tested based on emerging PK and safety data.

The DLT observation period is 1 cycle (21 days). All the AEs occurring during treatment, unless due to disease progression or to a cause obviously unrelated to IMP, will be taken into consideration by the Sponsor and recruiting Investigators for the determination of the MTD and RP2D for the SAR442720 and adagrasib combination. The Study Committee will review the overall safety, PK/PD, and clinical activity data and in agreement with the Sponsor's Study Medical Manager, will decide the recommended dose for the expansion phase.

The Study Committee will be comprised of the Principal Investigator from each site involved in the dose escalation phase, clinical team members from the Sponsor (including at least the Study Medical Manager, Global Study Manager, and experts when appropriate such as Global Safety Officer, pharmacokineticists, and biostatisticians).

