4.1.2 Dose escalation

In Part-1 and Part-3A, dose escalation will follow mTPI2 design with a minimum of 3 participants evaluable for DLT in the first cycle. A participant will be considered evaluable for DLT assessment if he/she receives at least 4 out of the 6 planned doses of SAR442720 in the first cycle and completes the DLT observation period or if he/she experiences a DLT in the DLT observation period. A participant who is not DLT-evaluable will be replaced to achieve a minimum of 3 DLT-evaluable participants at the same cohort.

The actual dose selected at each dose escalation decision, and the MTD identified at the conclusion of the dose escalation phase, will be determined by the Study Committee, in agreement with the Sponsor's Study Medical Manager, which may select a dose at or below the model's recommendation and should not select a dose that is suggested to be over toxic by the model. The Study Committee will review the overall safety of all dose levels. More details in the model and its operating characteristics can be found in Appendix 11 ([Section 10.11](#)).

The adaptive dose escalation design is based on the boundaries generated from the mTPI2 design. The dose escalation will stop if the next recommended dose has been collectively evaluated in at least 2 previous escalation cohorts.

It is anticipated that in Part-1 12 to 18 DLT-evaluable participants and in Part-3A 15 to 30 DLT-evaluable participants will be enrolled in the dose escalation. The actual total number of participants required will depend on the number of dose levels evaluated and on the incidence and timing of observed DLTs.

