- D) If the current dose is the highest dose and the rule indicates dose escalation, treat the new participants at the highest dose. If the decision based on the new cohort at the highest dose still recommends dose escalation, new dose levels may be explored.
- E) If at least 6 participants were treated at the recommended dose level, then this dose level will be the MTD.
- F) Skipping dose is not allowed.

Table 15 - Dose escalation rule of the modified toxicity probability interval-2 method

E: Escalate to the next higher dose, S: Stay at the current dose, D: De-escalate to the next lower dose and the current dose will never be used again because unacceptable high toxicity

a "D" will not be applied for first cohort of dose level 1 as the exception, however "DU" will give priority to the exception, ie, if 3 out of 3 participants have DLT at the dose level 1, the study committee may add lower dose level to assess the safety.

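### Appendix 11 carries the Part-1 dose-finding comparison over to Part-3A without simulating Part-3A; it breaks down if the MTD is DL(-)1 or if DL3a is too toxic while DL3b is at target

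*Protocol*

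**What the plan says.** Protocol 4.1.2 applies mTPI2 to Part-1 and Part-3A and sends the reader to Appendix 11 for the design's operating characteristics.

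- **What was simulated.** Appendix 11 covers three SAR442720 levels (100, 140 and 200 mg), starting at 140 mg, under four scenarios. On the strength of the monotherapy results, "the scenario of dose level 1 being the MTD is not in the consideration".
- **What was concluded.** The chance of finding the correct MTD "is higher than any other dose level for all scenarios in mTPI2 design", both designs need roughly 9 participants, and 3+3 is too conservative. Because both designs treat doses as discrete, "the performance comparison will be considered similar for Part-1 and Part-3A".
- **What Part-3A is.** Table 14 lists six levels: DL(-)1 80 mg + 400 mg BID, DL1 100 + 400, DL2 140 + 400, DL3a 140 + 600, DL3b 200 + 400, DL4 200 + 600. Footnote a says that "DL3b is optional and may be recommended by the study committee according to the safety data before further escalating to DL4". Rule F in 4.2.1 says "Skipping dose is not allowed".
- **How many levels.** Protocol 4.1 assumes 5 combination levels. SAP 1.1 counts 6.
- **Exposure.** Protocol 2.3.1.5 says adagrasib may increase SAR442720 "exposure by up to 2-fold (mainly due to CYP3A inhibition".

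**The concern.** That both designs use discrete doses says nothing about the length of the ladder, its order or where the MTD may lie. Part-3A differs from Part-1 on all three.

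The monotherapy reason for leaving out a low MTD does not carry over. At the 2-fold ceiling, DL1 corresponds to 2 x 100 = 200 mg of monotherapy, the highest cleared dose. DL2 and DL3a correspond to 2 x 140 = 280 mg, and DL3b and DL4 to 2 x 200 = 400 mg. Section 2.3.1.5 also anticipates overlapping gastrointestinal toxicity. A low MTD is therefore a case to simulate.

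Table 15 moves to one next higher or one next lower dose. DL3a raises adagrasib and DL3b raises SAR442720, so neither is known to be the more toxic.

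The MTD and RP2D are the first primary objective of Part-3A, and about 40 Part-3B participants are treated at the RP2D. There is no DMC, so the Study Committee is the body that relies on these properties.

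**Working it through.** **1. Inputs.** From the documents: cohorts of 3 (the stated minimum), stop when the next recommended dose already has two cohorts, start at DL1. Assumed: Beta(1,1) prior, a dose excluded if P(rate > target) > 0.95, and all DLT curves. Three settings for the redacted target and interval were run: (a) 0.30, 0.25-0.35; (b) 0.30, 0.25-0.33; (c) 0.25, 0.20-0.30. With 3,000 to 5,000 trials per scenario, the Monte Carlo standard error is at most sqrt(0.5 x 0.5/3000) = 0.9 points.

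The settings differ mainly in what 1 DLT in 3 implies. The posterior is Beta(2,3), with F(x) = 6x² - 8x³ + 3x⁴. Unit probability mass in the stay interval against the interval just above:
- (a) (0.4370 - 0.2617)/0.10 = 1.753 against (0.6090 - 0.4370)/0.10 = 1.720: stay
- (b) (0.4015 - 0.2617)/0.08 = 1.747 against (0.5420 - 0.4015)/0.08 = 1.757: de-escalate
- (c) (0.3483 - 0.1808)/0.10 = 1.675 against (0.5248 - 0.3483)/0.10 = 1.765: de-escalate

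**2. Part-1 first.** Strict reproduction is impossible. Setting (a) gives a mean of 9.4-9.9 participants (3+3: 9.8-10.8), near the stated 9, and the correct level is most often selected in all four scenarios (62-81%). Settings (b) and (c) give 10.6-11.8, and the correct level is not the most often selected in Scenario 1 (38% and 46%). They fit the appendix less well.

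**3. Part-3A, ordered scenarios, setting (a).** Correct selection, with DL3a then DL3b as one ladder:

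| MTD | mTPI2 | 3+3 | Difference (points) |
|---|---|---|---|
| DL1 | 61% | 35% | 26 |
| DL2 | 49% | 30% | 19 |
| DL3a | 49% | 30% | 19 |
| DL3b, DL3a tolerated | 41% | 26% | 15 |
| DL4 or above | 55% | 28% | 27 |

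Mean size is 10-19 (3+3: 11-19). The comparison carries over here. Under (b) the advantage disappears (DL2 31% against 30%; DL3b 23% against 26%).

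**4. MTD at DL(-)1.** Curve 0.30/0.45/0.55/0.62/0.70 over DL(-)1, DL1, DL2, DL3a, DL4. Across the three settings, mTPI2 selects DL1 in 29-45% and DL(-)1 in 18-32%; 3+3 is correct in 34%. An over-toxic level is selected in about 30-52% against 17%. These rates count a second de-escalation signal at the lowest level as no MTD, in line with rule C. If that level were declared the MTD instead, correct selection at (a) would rise to 44%, and at (b) and (c) DL(-)1 would overtake DL1. Over-toxic selection would barely change.

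**5. DL3a 0.50, DL3b 0.30.** DL3b is selected in about 5-9% and DL2 in 55-61%. With DL3a at 0.48, 3+3 does no better at (a) (7% against 11% for mTPI2). So what fails here is the claim that the correct level is picked most often, not the ranking of the two designs.

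**6. All levels at 0.50 or more.** An MTD is declared in about 15-50%, depending on the setting (3+3: about 14-21%).

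**7. The passages side by side.** Footnote a makes DL3b optional; rule F forbids skipping. No passage says which level is next lower from DL4, or what a de-escalation or exclusion at DL3a means for DL3b. The planned 15-30 participants equal 5 x 3 to 5 x 6; six levels would give 18-36. Which five levels are meant is not stated.

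**The case against.** The sentence carries over a comparison, not absolute rates, and step 3 shows that comparison surviving on ordered ladders under the setting that fits Part-1. That stands, and it limits the point to specific cases.

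Lower over-selection by 3+3 also agrees with the appendix's own remark that 3+3 is the more conservative design. True, but the appendix treats that as a weakness. With a low MTD it is a safety advantage, and the appendix gives no rate for it.

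Rule B, a separate override on the observed DLT rate, was not in the main runs. With an assumed 33% cut-off, over-toxic selection at setting (a) falls from 52% to 31%, still above 17%. The all-toxic figure falls from 46% to 13-15%, like 3+3.

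The 2-fold increase is a ceiling, and both starting doses were lowered because of it. The committee may choose a lower dose, "should not select a dose that is suggested to be over toxic by the model", and sets the expansion dose from all safety, PK/PD and activity data. Simulated selections are output of the algorithm, not final decisions. All this softens the consequence, but none of it supplies the missing evaluation.

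Omitting a level labelled optional need not count as skipping, and the committee may add dose levels. The text on entry to DL3b is therefore silent rather than prohibitive. A reader might infer that DL3b cannot be tested after a de-escalation from DL3a; no passage says so.

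**Conclusion.** The point holds. Part-3A's operating characteristics were not evaluated, and the reason given for borrowing those of Part-1 does not cover a longer, partly unordered, two-drug ladder. The borrowed statements fail in two plausible cases under every setting tried: the MTD at DL(-)1 (over-toxic selection about 30-52% against 17%), and DL3a too toxic with DL3b at target (DL3b selected in about 5-9%). The sizes rest on assumed targets, intervals and DLT curves, and in the first case the accuracy ranking also rests on the reading of rule C. The redactions are not a defect. The missing simulation and the unreconciled passages do not depend on them.

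Three stronger readings are not supported:
- That the stated properties fail in Part-3A generally. They survive on ordered mid-range ladders at setting (a).
- That DL3b is nearly unreachable. If the committee always opts in after DL3a, it is tested in 73-92% when DL3a is tolerated and in 17% when only DL3a is too toxic.
- That a fixed share of all-toxic trials would still declare an MTD. That share is a range that depends on the setting.

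Nor is the figure of roughly 9 participants applied to Part-3A, for which 15-30 are planned.

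**What to change.** - Delete the sentence in Appendix 11 that carries Part-1 performance over, or restrict it to what has been simulated.
- Re-run Appendix 11 on the Part-3A levels with rules A to F, including rule B, and the Table 15 footnote. Add scenarios with the MTD at DL(-)1, the MTD at DL1, all levels too toxic, DL3a the more toxic, and DL3b the more toxic. Report correct-selection and over-toxic-selection rates for both designs.
- Reconcile Table 15, rule F, Table 14 footnote a, and the 5-level (Protocol 4.1) and 6-level (SAP 1.1) statements, so that they agree on how DL3a, DL3b and DL4 are handled. No dose, order or clinical rule is proposed here.

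Cost: about a day of simulation and some wording in Protocol 4.1, 4.2.1 and Appendix 11 and in SAP 1.1, with no extra participants. The stated performance will look less favourable.

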10.13 APPENDIX 13: MENUS AND COMPOSITION FOR FOOD EFFECT STUDY

Table 28 - Option 1: Moderate-Calorie, Moderate-Fat Breakfast, Non-Vegan

Item	Qty	U/M	Cals (kcal)	Fat (g)	Prot (g)	Carb (g)
Wheat bread ^a	2	Slice	120	1.0	8.0	22.0
Skippy peanut butter pouch ^b	1	Packet	200	16.0	7.0	6.0
Grape or strawberry jelly ^c	3	Packet	105	0.0	0.0	27.0
Banana, fresh, medium, 7" – 7-7/8"	1	Each	105	0.39	1.29	26.95
2% milk	8	Ounce	130	5.0	8.0	12.0
Total (g)			660	22.39	24.29	93.95
Calories (kcal)			-	201.51	97.16	375.80
Percent by calories			-	29.9%	14.4%	55.7%

Abbreviations: Carb, carbohydrate; Cals, calories; Prot. Protein; Qty, quantity.

a Nature's Own 100% whole wheat bread OR Wonder 100% whole wheat bread.

b A Skippy creamy peanut butter individual packet, 32 g (or measure 1.12 oz out of a jar) OR Jif creamy peanut butter, red cap (measure 1.12 Oz out of a jar).

c A Smucker's individual packet of grape or strawberry jelly, 0.5 oz packet, OR Heinz concord grape or strawberry jelly, 0.5 Oz packet.

Table 29 - Moderate-Calorie, Moderate-Fat Breakfast, Vegan

Item	Qty	U/M	Cals (kcal)	Fat (g)	Prot (g)	Carb (g)
Wheat Bread ^a	2	Slice	120	1.0	8.0	22.0
Skippy Peanut Butter Pouch ^b	1	Packet	200	16.0	7.0	6.0
Grape or Strawberry Jelly ^c	2	Packet	70	0.0	0.0	18.0
Banana, fresh, medium, 7 – 7-7/8"	1	Each	105	0.39	1.29	26.95
Vanilla soy milk, silk ^d / vanilla soy milk, great value ^e	8 / 12	Ounce / Ounce	130 / 133	3.5 / 4.4	6.0 / 8.9	18.0 / 16.3
Total (g)			625	20.89	22.29	90.95
Calories (kcal)			-	188.01	89.16	363.80
Percent by calories			-	29.3%	13.9%	56.8%

Abbreviations: Carb, carbohydrate; Cals, calories; Prot. Protein; Qty, quantity.

a Nature's Own 100% whole wheat bread OR Wonder 100% whole wheat bread.

b Skippy Creamy peanut butter individual packet, 32 g (or measure 1.12 oz out of a jar) OR Jif creamy peanut butter, red cap (measure out of jar 1.12 Oz).

c A Smucker's individual packet of grape or strawberry jelly, 0.5 oz packet OR Heinz concord grape or strawberry jelly, 0.5 oz packet.

d A Silk brand (very vanilla), 8 oz OR Great Value brand (organic vanilla), 12 oz.

e For the vegan option, the total, calories, percent by calories, are based on silk vanilla soy milk.

